7.4 Progression-Free Survival (PFS)

PFS will be calculated for each patient as the number of days from the first day of treatment to the date of the first documented disease progression/relapse or date of death, whichever occurs first. The exact date of disease progression is based on the tumor response assessment dates as indicated in Section 7.1.1. If disease progression/relapse does not occur, PFS is censored as of the date of their last imaging exam of target or non-target lesions. However, for patients without an assessment of disease progression/relapse who escalate to a higher dose, PFS is censored as of the date of their first dose of study medication in the later dose cohort. Patients without an assessment of disease progression/relapse who discontinue the study and indicate progressive disease or clinical progression as the primary reason for ending treatment will be counted as having progressed on their last dose date of BBT-176—whichever date is earlier.

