##### **5.3.2.2 Secondary Endpoints**

- DoR and PFS per RECIST version 1.1
- Safety and tolerability (incidence of AEs)
- Plasma BBT-176 concentrations at steady state

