## **12.8      Safety Monitoring Committee**

The study will be monitored by an SMC comprised of the PI for each site, the CRO Medical Monitor, and a Sponsor representative(s) or designee. During the trial, all SAEs and potential DLTs, as well as any PK results, will be sent to the SMC on a continual basis. The SMC may choose more conservative dosing decisions or stopping rules for the dose-escalation cohorts. The patients who exercised the option of intra-patient dose escalation will be monitored by the SMC as well. Ad hoc SMC meeting may be convened to discuss potential DLT cases more in depth.

In Part 1 of the trial (dose-escalation cohorts), the SMC will decide the dose of BBT-176 for the next cohort, as well as define the MTD, based on available PK, statistical assistance tool (BLRM or mTPI-2), safety findings. The RP2D may be set lower than the MTD if there are concerns about tolerability or if the analysis of biomarker and pharmacodynamic data suggests a lower dose would be appropriate.

In RP2D exploratory cohort, SMC will make balanced evaluation and recommendation about RP2D based upon safety, PK, efficacy including biomarker data.

When clinical data of at least six patients are available from each of two subgroups of this cohort, then SMC will convene and review; will recommend the Sponsor to continue or discontinue each of these cohorts.

When clinical data of at least twelve patients are available from each of two subgroups , then SMC will convene and review; will recommend to the Sponsor, RP2D for further evaluation in Part 2.

Even after RP2D is determined, the Sponsor may continue to enroll patients into RP2D exploratory cohort up to 30 patients in each cohort.

In Part 2 of the trial (enrichment), the SMC will continually review the safety of BBT-176.

The SMC will assess safety data and operate under the rules of an approved charter that will be written and reviewed at the inception of the SMC. At that time, each data element that the SMC needs to assess will be clearly defined. The SMC will provide its input to the Sponsor and CRO as needed.

Further information describing the SMC scope and procedures will be provided in the SMC Charter.

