2.1.2 Secondary Objectives

Table 3 shows the secondary objectives and endpoints of Part 1 [REDACTED].

Table 3. Secondary Objectives and Endpoints

Part 1 Secondary Objectives	Endpoints

 To characterize the PK profile of BBT-176 after a single oral dose and steady state after multiple doses when given orally alone and in combination with cetuximab 	
 Plasma concentrations of BBT-176 PK parameters ($t_{1/2}$, C_{max}, t_{max}, AUC, C_{trough})

 To evaluate the anti-tumor activity of BBT-176 in selected mutant types by evaluation of the ORR using RECIST version 1.1 	
 ORR per RECIST version 1.1
---	--

Table 4 shows the secondary objectives and endpoints of Part 2 [REDACTED]

Table 4. Secondary Objectives and Endpoints

Part 2 Secondary Objectives	Endpoints

 To evaluate the anti-tumor activity of BBT-176 in selected mutant types by evaluation of the Duration of Response (DoR) and the Progression-Free Survival (PFS) using RECIST version 1.1 	
 DoR per RECIST version 1.1 PFS per RECIST version 1.1

 To evaluate the safety and tolerability of BBT-176 at the PR2D 	
 Incidence of adverse events [AEs] and clinical laboratory abnormalities defined as DLTs

 To characterize the snapshot PK of BBT-176 at steady state after multiple oral doses 	
 Plasma BBT-176 concentrations at steady state PK parameters (C_{max}, t_{max})

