7.7 Methods of Efficacy Analysis

The extent of disease will be assessed using the sum of the longest diameter from the target lesions. Change from baseline and percent change from baseline measurements will be summarized at each scheduled evaluation using descriptive statistics.

The investigators' assessments of patients' target lesion response, non-target lesion response, and appearance of new lesions (collected from the eCRF) are used to determine the overall [tumor] response at each time point as shown in Section 7.1.1. The investigators' assessments will be shown in listings.

Next, as indicated in Section 7.1.2, the best [tumor] response for sequential pairs (or triplets) of time point responses (recorded from the start of study treatment until the end of treatment) are determined as shown in Table 14 and in the subsequent discussion. Finally, as indicated in Section 7.1.3, the Best Overall Response for a patient—when confirmation of CR and PR are required—is the best of these Best Responses. The number and percent of patients in each category of Best Overall Response (CR, PR, SD, and PD) will be summarized by cohort.

The ORR will be presented with frequencies and percentages with 80% confidence interval. The frequency and percentages of patients with a best overall response of CR, PR, with stable disease (SD), or with PD will be summarized by cohort, additionally. 80% confidence intervals will be provided.

DoR will be summarized using the Kaplan-Meier estimate including median estimate, first quartile, 3rd quartile.

Progression-free survival in days will be summarized using the Kaplan-Meier to estimate the median PFS. The quartiles, including the median time-to-event and its two-sided 95% CI will be presented for each endpoint. Summaries will be presented for each cohort and overall.

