Note: When nodal disease is included in the sum of target lesions and the nodes decrease to “normal” size (< 10 mm), they may still have a measurement reported on scans. This measurement should be recorded even though the nodes are normal in order not to overstate progression should it be based on increase in size of the nodes. As noted earlier, this means that patients with CR may not have a total sum of “zero” in the eCRF.

In trials where confirmation of response is required, repeated ‘NE’ time point assessments may complicate best response determination. The analysis plan for the trial must address how missing data/assessments will be addressed in determination of response and progression. For example, in most trials it is reasonable to consider a patient with time point responses of PR-NE-PR as a confirmed response.

Patients with a global deterioration of health status requiring discontinuation of treatment without objective evidence of disease progression at that time should be reported as “symptomatic deterioration”. Every effort should be made to document objective progression even after discontinuation of treatment. Symptomatic deterioration is not a descriptor of an objective response: it is a reason for stopping trial therapy.

In some circumstances it may be difficult to distinguish residual disease from normal tissue. When the evaluation of complete response depends upon this determination, it is recommended that the residual lesion be investigated (fine needle aspirate/biopsy) before assigning a status of complete response. FDG-PET may be used to upgrade a response to a CR in a manner similar to a biopsy in cases where a residual radiographic abnormality is thought to represent fibrosis or scarring. The use of FDG-PET in this circumstance should be prospectively described in the protocol and supported by disease-specific medical literature for the indication. However, it must be acknowledged that both approaches may lead to false positive CR due to limitations of FDG-PET and biopsy resolution/sensitivity.

For equivocal findings of progression (e.g., very small and uncertain new lesions; cystic changes, or necrosis in existing lesions), treatment may continue until the next scheduled assessment. If at the next scheduled assessment, progression is confirmed, the date of progression should be the earlier date when progression was suspected.

CONFIRMATORY MEASUREMENT/DURATION OF RESPONSE

Confirmation

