In non-randomized trials where response is the primary endpoint, confirmation of PR and CR is required to ensure that the identified responses are not the result of measurement error. This will also permit appropriate interpretation of results in the context of historical data where response has traditionally required confirmation in such trials. However, in all other circumstances, i.e., in randomized trials (phase 2 or 3) or trials where stable disease or progression are the primary endpoints, confirmation of response is not required since it will not add value to the interpretation of trial results. However, elimination of the requirement for response confirmation may increase the importance of central review to protect against bias, in particular in trials which are not blinded.

In the case of SD, measurements must have met the SD criteria at least once after trial entry at a minimum interval (in general not less than 6 to 8 weeks) that is defined in the trial protocol.

Duration of Overall Response

The duration of overall response is measured from the time that measurement criteria are first met for CR/PR (whichever is first recorded) until the first date that recurrent or progressive disease is objectively documented (taking as reference for progressive disease the smallest measurements recorded on study).

The duration of overall complete response is measured from the time measurement criteria that are first met for CR until the first date that recurrent disease is objectively documented.

Duration of Stable Disease

Stable disease is measured from the start of the treatment (in randomized trials, from date of randomization) until the criteria for progression are met, taking as reference the smallest sum on study (if the baseline sum is the smallest, this is the reference for calculation of PD).

The clinical relevance of the duration of stable disease varies in different studies and diseases. If the proportion of patients achieving stable disease for a minimum period of time is an endpoint of importance in a particular trial, the protocol should specify the minimal time interval required between two measurements for determination of stable disease.

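### SAP 7.3 and 7.4 date progression without an assessment by an earlier-of rule that names only one date, and count clinical progression under DoR and PFS labels that say RECIST 1.1

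*SAP*

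**What the plan says.** SAP 7.3 (DoR) and SAP 7.4 (PFS) close with the same rule. It covers patients who have no progression assessment, leave the study, and give progressive disease or clinical progression as the main reason for ending treatment. They are events, and they "will be counted as having progressed on their last dose date of BBT-176—whichever date is earlier". The sentence is complete and not redacted.

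Other visible text bears on it:

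- SAP 7.3 includes clinical progression in the DoR event definition. SAP 7.4 defines the PFS event as documented progression or death, takes progression dates from tumor assessments, and admits clinical progression only through the closing rule.
- The endpoint label is "DoR and PFS per RECIST version 1.1" in Protocol 5.3.2.2, and "PFS per RECIST version 1.1" in SAP Table 4. SAP Table 5 uses the same label for Part 1.
- SAP Appendix 2 runs duration of response "until the first date that recurrent or progressive disease is objectively documented". It also says: "Symptomatic deterioration is not a descriptor of an objective response: it is a reason for stopping trial therapy".
- SAP 7.7 sets the outputs: "Progression-free survival in days will be summarized using the Kaplan-Meier to estimate the median PFS", and "DoR will be summarized using the Kaplan-Meier estimate including median estimate, first quartile, 3rd quartile".
- SAP 7.1 has scans every 6 weeks until progression, EOT or new anti-cancer treatment. Protocol 10.1.1 keeps scans on their original schedule when study drug is delayed.

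**The concern.** There are two separate faults.

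First, an earlier-of rule needs two dates and this one supplies one. Leaving the study is mentioned, but no date is attached to it. Two programmers could date the same patients differently, and in an open-label trial the choice could be made after outcomes are known.

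Second, someone reading a PFS or DoR table labelled RECIST 1.1 would expect progression shown on imaging. The planned analysis also contains clinical progression with no qualifying assessment. Whether these patients are events or are censored can move the reported median, so the label should say which was done.

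**Working it through.** **1. What the missing date could be.**

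- *Study discontinuation.* The Protocol's schedule of activities (Section 3.3) puts EOT on the last day of study treatment, with safety follow-up afterwards. Last dose is then practically always the earlier date, and the clause does nothing.
- *Last imaging exam.* This is the censoring date in both sections. Affected events would move back to a scan that showed no progression.

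**2. Order of dates.** Scans continue during a dose hold. A patient whose dosing is held and never resumed can therefore have a scan without progression after the last dose. The rule would place progression before that scan. For DoR, if that scan is the first to show response, the event would precede the response it is meant to end. The documents do not show how often this would happen.

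**3. Label against rule.**

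| Endpoint | Label | Appendix 2 | SAP rule |
|---|---|---|---|
| DoR | RECIST 1.1 | Ends at objectively documented progression | Clinical progression counts |
| PFS | RECIST 1.1 | No PFS definition in the visible text | Clinical progression counts, through the closing rule only |

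The conflict is explicit for DoR. For PFS it rests on the label and on 7.4's own requirement that progression be documented. Protocol 6.3.1 also lists symptomatic progression separately from RECIST-defined progression as a reason to end treatment.

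**4. Size for PFS.** The plan gives no figure to reproduce.

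*From the documents:* scan interval 6 × 7 = 42 days (SAP 7.1). Sample size 30 comes from Protocol 12.8: "the Sponsor may continue to enroll patients into RP2D exploratory cohort up to 30 patients in each cohort". That cap is for a Part 1 exploratory cohort, so it is only illustrative for Part 2.

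*Assumed:* exponential time to progression T with median m of 60, 90, 120 or 180 days; a share p of 10, 20 or 30% of progressions without an assessment; last dose on day T; no other censoring.

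Let λ = ln 2 / m and q = exp(−42λ). Assessed progressions become events at the next scan.

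Mean gap from last scan to last dose = 1/λ − 42/(exp(42λ) − 1):
- m = 60: 86.56 − 67.25 = 19.3 days
- m = 180: 259.69 − 239.25 = 20.4 days

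Large-sample Kaplan-Meier curves, with k the number of scans so far:
- event at last dose: S(t) = p·exp(−λt) + (1 − p)·q^k
- event at last scan: S(42k) = p·q^(k+1) + (1 − p)·q^k
- censored at last scan: S(42k) = [q / (1 − p(1 − q))]^k

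Example, m = 90 and p = 20%: q = 0.7236, q² = 0.5237, q³ = 0.3789.
- Last scan: at day 84, 0.2 × 0.3789 + 0.8 × 0.5237 = 0.495, so the median is 84.
- Last dose: 0.2·exp(−λt) = 0.5 − 0.4189 gives t = 117.
- Censored: the factor is 0.7236/0.9447 = 0.766; its square is 0.587 and its cube 0.449, so the median is 126.

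| True median | Share p | Event at last dose | Event at last scan | Censored at last scan |
|---|---|---|---|---|
| 60 | 10, 20, 30% | 84 | 84 | 84 |
| 90 | 10% | 126 | 126 | 126 |
| 90 | 20% | 117 | 84 | 126 |
| 90 | 30% | 105 | 84 | 126 |
| 120 | 10, 20, 30% | 126 | 126 | 168 |
| 180 | 10% | 210 | 210 | 210 |
| 180 | 20, 30% | 210 | 210 | 252 |

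The choice of date leaves the large-sample median unchanged in 10 of 12 scenarios. Counting versus censoring moves it by 0 to 42 days. At m = 180 and p = 30% the censored curve is 0.499 on day 252, so that entry is borderline.

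Simulated trials of 30 patients:
- Last dose versus last scan: the median differs in about 8–29% of trials, by about 20–22 days when it differs and by at most 42.
- Event at last dose versus censored at last scan: the median differs in about 24–92% of trials, and the shift averages about 8–91 days over all trials.

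**5. Why this does not transfer to DoR.** DoR uses responders only, so a 30-patient cohort gives 30 DoR times only if everyone responds. SAP 7.1.2 and 7.1.3 also describe best response when confirmation is required. If the next 42-day scan confirms a response, there are no events in the first interval, where the exponential model puts 1 − q = 38% (m = 60) to 15% (m = 180) of them.

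I re-ran with no event before day 42, the same overall medians and 30 responders. At m = 60 the two dates give different medians in well under 1% of trials, and counting versus censoring shifts the median by 0 to 0.3 days. At m = 180 and p = 30% that shift is about 70 days instead of about 91. At medians of 90–180 the date choice still matters in about 9–30% of trials.

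**The case against.** The best defence is that the dropped comparator is study discontinuation. Last dose then governs, there is no numerical consequence, and the clause is an editing slip. That may well be right, and it is why the date ambiguity carries little weight. It does not justify keeping a clause that either does nothing or means something else, and it leaves the ordering problem under dose holds untouched.

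The second defence is that counting clinical progression is a legitimate choice, stated in the SAP, and that Appendix 2 is reproduced general guidance. This also stands in part. A reader might infer that the SAP conceals these events or that counting them is wrong; neither follows, because 7.3 and 7.4 state the rule openly. What remains is a label that does not match it, more clearly for DoR than for PFS.

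A reader might also apply the PFS figures to DoR. Step 5 shows why that fails. Nor is the Part 2 primary endpoint touched: ORR does not use this dating rule.

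Finally, the 10–30% share has no source in the documents. The patients concerned may have had earlier scans without progression; the SAP says only that they lack a progression assessment.

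**Conclusion.** Both faults hold, at minor severity. The dating sentence is incomplete, and under dose holds it can place an event before a scan without progression or, for DoR, before the response. The label does not disclose clinical events.

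The missing date matters little: not at all if it is study discontinuation, and about 20 days per affected event if it is the last scan. Event versus censored status matters more for PFS, on the assumed distribution, medians and shares above. No DoR magnitude is claimed from the PFS figures. Only Part 2 secondary and Part 1 exploratory endpoints are affected.

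Protocol 11.6.2 and 11.6.3, SAP 7.6, the response table in SAP 7.1.1, the assessment schedules and the SAP Appendix 1 date conventions are redacted or not shown. Imaging at EOT, which would reduce the affected share, or an existing sensitivity analysis therefore cannot be excluded. Neither would complete the visible sentence.

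**What to change.** In SAP 7.3 and 7.4:

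- **Date.** Delete the closing earlier-of clause and use the last dose date. Add that if a scan without progression, or the response date for DoR, falls after the last dose, the event is dated at that scan. Say openly that this exception departs from the present earlier-of wording.
- **Label.** Call the planned analysis *RECIST or clinical progression or death* and keep it as the main one. Add one sensitivity table per endpoint for *RECIST-documented progression or death*.

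The cost is a few sentences and two tables. The drawback is that the RECIST-only result is biased upward if scans stop at EOT, because patients who stop for clinical progression are then censored just as they deteriorate. It should carry that note and not be read alone. The changes should be made before the analysis is run.

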7.5 Handling Missing, Unused, and Spurious Data

All available efficacy data will be included in the data listings and tabulations. No imputation of values for missing data will be performed.

7.6 [REDACTED]

[REDACTED]

[REDACTED]

[REDACTED]

[REDACTED]

7.7 Methods of Efficacy Analysis

The extent of disease will be assessed using the sum of the longest diameter from the target lesions. Change from baseline and percent change from baseline measurements will be summarized at each scheduled evaluation using descriptive statistics.

The investigators' assessments of patients' target lesion response, non-target lesion response, and appearance of new lesions (collected from the eCRF) are used to determine the overall [tumor] response at each time point as shown in Section 7.1.1. The investigators' assessments will be shown in listings.

Next, as indicated in Section 7.1.2, the best [tumor] response for sequential pairs (or triplets) of time point responses (recorded from the start of study treatment until the end of treatment) are determined as shown in Table 14 and in the subsequent discussion. Finally, as indicated in Section 7.1.3, the Best Overall Response for a patient—when confirmation of CR and PR are required—is the best of these Best Responses. The number and percent of patients in each category of Best Overall Response (CR, PR, SD, and PD) will be summarized by cohort.

The ORR will be presented with frequencies and percentages with 80% confidence interval. The frequency and percentages of patients with a best overall response of CR, PR, with stable disease (SD), or with PD will be summarized by cohort, additionally. 80% confidence intervals will be provided.

DoR will be summarized using the Kaplan-Meier estimate including median estimate, first quartile, 3rd quartile.

Progression-free survival in days will be summarized using the Kaplan-Meier to estimate the median PFS. The quartiles, including the median time-to-event and its two-sided 95% CI will be presented for each endpoint. Summaries will be presented for each cohort and overall.

8. PHARMACOKINETIC (PK) ANALYSES

All pharmacokinetic analyses will be based on the PK populations. This SAP describes the method of deriving PK using non-compartmental analysis applying appropriate software, i.e., Phoenix™

WinNonlin® (Version 8.0 or higher, Certara Corporation), and all other analyses and summaries using SAS® (Version 9.4 or higher, SAS Institute Inc.).

The PK analyses will be conducted for BBT-176 in plasma, will include a listing, summary, and figure of concentrations, and derived PK parameters as described below.

8.1 PK Sampling Schedule

Plasma samplings for PK analyses will be done according to [REDACTED]

8.2 Handling of the Below the Lower Limit of Quantification (BLQ) and the No Reportable Concentration Values

[REDACTED]
[REDACTED]
[REDACTED]
[REDACTED]
[REDACTED]
[REDACTED]
[REDACTED].

Subjects for whom there are insufficient data to calculate the PK parameters will be included in the concentration tables only and will be excluded from the PK and statistical analysis.

[figure not shown]
